3.5.2 Selection of Endpoints

The present trial has been designed as a non-inferiority trial with number of oocytes retrieved as the primary endpoint reflecting the pharmacological effect of FSH on follicular development and growth. Known pharmacological effects of FSH are associated with risks of developing OHSS.

Oocytes retrieved is commonly used as primary endpoint for this kind of drugs. The set of secondary endpoints is considered appropriate for an efficacy trial and includes items of special interest related to controlled ovarian stimulation. Safety will be closely monitored and the frequency of OHSS (early, late, and total) is included.

3.5.3 Blinding

The two investigational medicinal products (IMPs) differ in presentation. GONAL-F is manufactured by Merck Serono and bought commercially for use in this phase 3b trial. A double-blind, double-dummy design is not considered feasible. The trial, however, is assessor-blind, ensuring unbiased evaluation by the investigators and other assessors such as embryologists.

One or more trial medication delegate(s) will be identified at each site. The trial medication delegate will be responsible for all trial medication related issues, both practically at the clinic and in interactions with the subject. To maintain the assessor-blinding, the trial medication delegate is not allowed to perform any assessments in the trial. Information on treatment allocation is only available to the trial medication delegate. The investigator does not have access to these modules in the electronic data capture (EDC) system. Thus, only the trial medication delegate at the site, the monitors and the participating subjects will know the treatment allocation once the subjects are randomised. Precaution will be taken to ensure that the treatment allocations are not available to the investigators or other assessors throughout the trial. Subjects will be clearly instructed to only discuss their treatment allocation with the trial medication delegate, and to not mention it to the investigator.

Drug accountability forms and other forms identifying treatment allocation are kept unavailable to the investigator. The subject will during the informed consent process be informed, both verbally and in writing, to not disclose her treatment allocation to the investigator. Trial staff is provided training in the importance of maintaining blinding, and trial medication delegates are also helped to set up systems at the clinic.

The trial medication delegate will dispense the trial medication to the subject (and may also do the actual administration at the clinic, if required). The investigator will, based on the follicular development, judge if dose adjustments are recommended and state his/her directions on a form developed for that purpose, which will be used to inform the trial medication delegate. Depending on whether the subject is being treated with FE 999049 or GONAL-F, the trial medication delegate will provide detailed instructions to the subject in line with the dosing regimen for each preparation as outlined in the protocol. In other words, if the investigator recommends a dose adjustment, the

trial medication delegate will implement a decrease or increase of 5 µg per day as applicable if the subject is in the FE 999049 group, or of 75 IU per day as applicable if the subject is in the GONAL-F group. Requests for cycle cancellation due to inappropriate response or other medical reasons are followed, irrespective of treatment group.

The Ferring clinical trial team will be blinded to treatment allocation until breaking of the blind. Delegated functions that need access to treatment allocation to fulfil their responsibilities are exempted. Details are provided in a trial-specific Blinding Plan.

3.5.4 Selection of Doses in the Trial

The proposed dosing regimen for FE 999049 in the submitted application in China is based on each woman's serum AMH concentration and her body weight, and is a fixed-dose regimen with the daily dose maintained throughout the stimulation period. Proposed maximum daily dose of FE 999049 is 12 µg for the first treatment cycle and 24 µg in subsequent treatment cycles.

Approved starting doses of GONAL-F for ART in China, 150-225 IU fixed for the initial days of stimulation followed by the possibility for subsequent dose adjustments with a maximum daily dose of 450 IU, provided a reference point for evaluating the ovarian response observed with FE 999049.

Based on clinical trial data from more than 1,500 patients undergoing controlled ovarian stimulation with individualised FE 999049 dosing regimen in a GnRH antagonist protocol, it has been possible to establish the daily FE 999049 dose that provides a comparable ovarian response (i.e. number of oocytes retrieved and number of follicles \geq 12 mm and serum estradiol at end-of-stimulation) as 150 IU/day GONAL-F.³¹ These clinical trial data suggest that a daily dose of 10.0 [95% CI 9.2; 10.8] µg FE 999049 provides an ovarian response equal to that obtained with 150 IU GONAL-F. Applying this dose equivalence factor, it is extrapolated that 15 µg/day FE 999049 will provide an ovarian response comparable to that obtained with 225 IU/day GONAL-F. The dose equivalence factor between FE 999049 and GONAL-F was confirmed in 759 Chinese patients in Trial 000145, for whom 10.2 [95% CI: 9.3–11.2] µg FE 999049 provided an equal ovarian response to that obtained with 150 IU GONAL-F.³²

The starting dose of 15 µg FE 999049 has not previously been evaluated in the Chinese population. In this population, subjects undergoing a first treatment cycle have been exposed to a maximum of 12 µg FE 999049 (Trial 000145). In other populations, subjects undergoing repeated treatment cycles have been exposed to a maximum of 24 µg FE 999049 without any safety concerns (Trial 000071).¹

In the current trial, the choice of starting dose level (10 µg FE 999049 / 150 IU GONAL-F or 15 µg FE 999049 / 225 IU GONAL-F) is based on the investigator's clinical judgement. The distribution of starting doses in the trial population will thereby reflect the distribution of starting doses used in clinical practice. After the first 5 days with stimulation at a fixed dose, the dose may be increased or decreased based on the subject's ovarian response by 5 µg FE999049 or 75 IU GONAL-F which are considered doses of similar magnitude based on the extrapolation described above. Dose

adjustments may be implemented not more frequently than once every 2 days. This possibility for a gradual increase in dose and a maximum dose of 20 µg/day FE 999049 or 300 IU/day GONAL-F for a maximum duration of 20 days constitutes a safe approach for the subjects. The starting dose level of GONAL-F is in line with labelling recommendations.²⁰

The doses of overall treatment regimens for the GnRH agonist, hCG, and progesterone products are in line with the recommendations in the respective products' labelling for the indication of ART and/or standard clinical practice.

3.5.5 Selection of Trial Population

This trial will include women who have been diagnosed with tubal infertility, unexplained infertility, endometriosis stage I/II, or have partners diagnosed with male factor infertility, and who are considered eligible for IVF or ICSI. The trial will include women up to 40 years of age and will thereby cover the patient age span in which most ART treatments are performed. The allowed body mass index (BMI) is 17.5-32.0 kg/m², thus including underweight, normal weight, overweight and obese subjects.

Because the ovarian stimulation treatment is to be performed using a GnRH agonist protocol, only patients with a serum AMH concentration of ≤ 35 pmol/L are to be included to avoid exposing patients with a high ovarian reserve to an increased risk of developing excessive response or OHSS.

The exclusion criteria incorporate the contraindications for the use of gonadotropins and other concomitant fertility medications used in the trial.

Altogether, the population selected for this trial would be expected to be representative for subjects undergoing controlled ovarian stimulation in IVF or ICSI cycles in China.

4 SELECTION OF TRIAL POPULATION

4.1 Trial Population

4.1.1 Inclusion Criteria

Subjects must meet all of the criteria below to be eligible for participation on this trial.

1. Signed and dated Informed Consent Form for participation in the trial, obtained before any trial-related procedures.
2. Signed and dated Informed Consent Form for data collection on the neonate, obtained before randomisation to treatment.
3. In good physical and mental health in the judgement of the investigator.
4. Chinese pre-menopausal female between the ages of 20 and 40 years; at least 20 years (including the 20th birthday) when signing the informed consent and no more than 40 years (up to the day before the 41st birthday) at the time of randomisation.
5. Eligible for ovarian stimulation with a dose equivalent to 150 IU GONAL-F or 225 IU GONAL-F, as judged by the investigator.
6. Body mass index (BMI) between 17.5 and 32.0 kg/m² (both inclusive) at screening.
7. Infertile women diagnosed with tubal infertility, unexplained infertility, endometriosis stage I/II or with partners diagnosed with male factor infertility, eligible for in vitro fertilisation (IVF) or intracytoplasmic sperm injection (ICSI) using fresh or frozen ejaculated sperm from male partner or sperm donor.
8. Infertility for at least one year before randomisation for subjects <35 years or for at least 6 months for subjects ≥35 years (criteria not applicable in case of tubal or severe male factor infertility).
9. Regular menstrual cycles of 24-35 days (both inclusive), presumed to be ovulatory.
10. Transvaginal ultrasound documenting presence and adequate visualisation of both ovaries, without evidence of significant abnormality (e.g. no endometrioma greater than 3 cm, and no enlarged ovaries or ovarian cyst not due to polycystic ovarian syndrome, which would contraindicate the use of gonadotropins) and normal adnexa (e.g. no hydrosalpinx) within 1 year prior to randomisation. Both ovaries must be accessible for oocyte retrieval.
11. Early follicular phase (cycle day 2-4) serum levels of follicle-stimulating hormone (FSH) between 1 and 15 IU/L (results obtained within 3 months prior to randomisation).
12. Serum anti-Müllerian hormone (AMH) concentration of ≤35 pmol/L at screening.
13. Confirmation of downregulation prior to randomisation, defined as fulfilling all of the following criteria:
 - a. menstrual bleeding
 - b. shed endometrium with a thickness <5 mm observed by transvaginal ultrasound
 - c. no ovarian follicles ≥10 mm (including cysts that cannot be punctured prior to stimulation) observed by transvaginal ultrasound

4.1.2 Exclusion Criteria

Subjects meeting any of the criteria listed below will not be eligible for participation in this trial.

1. Primary ovarian failure.
2. Known endometriosis stage III-IV (defined by the revised ASRM classification, 1996).
3. More than three previous controlled ovarian stimulation cycles initiated, regardless of outcome.
4. History of previous episode of ovarian hyperstimulation syndrome (OHSS), exuberant ovarian response to gonadotropins, or polycystic ovarian syndrome.
5. Known endocrine or metabolic abnormalities (pituitary, adrenal, pancreas, liver or kidney) which can compromise participation in the trial with the exception of controlled thyroid function disease.
6. Known tumours of the ovary, breast, uterus, adrenal gland, pituitary or hypothalamus which would contraindicate the use of gonadotropins.
7. Fibroid tumours of the uterus incompatible with pregnancy.
8. Currently breast-feeding.
9. Undiagnosed vaginal bleeding.
10. Findings at the gynaecological examination at screening which preclude gonadotropin stimulation or are associated with a reduced chance of pregnancy, e.g. congenital uterine abnormalities or retained intrauterine device.
11. Pregnancy (negative urinary pregnancy tests must be documented at screening and before randomisation to treatment) or contraindication to pregnancy.
12. Use of fertility modifiers during the last menstrual cycle before randomisation, including dehydroepiandrosterone (DHEA) or cycle programming with oral contraceptives, progestogen or estrogen preparations.
13. Known inherited or acquired thrombophilia disease.
14. Active arterial or venous thromboembolism or severe thrombophlebitis, or a history of these events.
15. Known porphyria.
16. Hypersensitivity to any active ingredient or excipients in the medicinal products used in the trial.
17. Previous participation in the trial.
18. Use of any non-registered investigational drugs during the last 3 months prior to randomisation.

4.2 Method of Assigning Subjects to Treatment Groups

4.2.1 Recruitment

The participating subjects will be recruited among the patients attending the clinics included in the trial. Advertisements may be used if approved by the local ethics committee and regulatory authorities, as applicable according to local regulations.

A screening number is allocated to each subject who has given written informed consent to participate in the trial. A subject must always be assigned to the lowest available screening number at each site. A screening log of all screened subjects must be maintained by the investigator.

4.2.2 Randomisation

Once downregulation is confirmed, subjects will within 7 days be randomised in a 1:1 ratio to FE 999049 or GONAL-F and stimulation will be initiated. Randomisation will be stratified according to the investigator's assessment of an appropriate starting dose (10 µg FE 999049 / 150 IU GONAL-F or 15 µg FE 999049 / 225 IU GONAL-F). Randomisation is performed centrally through the interactive response technology (IRT) system. The randomisation number will be allocated to the subject together with the treatment allocation and starting dose. When a subject is randomised to the trial, she will always be assigned to the lowest available randomisation number within site and stratum. An independent statistician at the Ferring Global Biometrics Department will prepare a computer-generated randomisation list and randomisation is performed in blocks. Blocks will be maintained within trial sites, i.e. the randomisation will be stratified by trial site. The block size will only be revealed when the trial database is declared clean and locked. An overview of recruitment will be recorded on a subject identification code list for all randomised subjects kept by the investigator.

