3.2 Planned Number of Trial Sites and Subjects

An approximate number of 300 subjects is planned for randomisation (150 subjects to treatment with FE 999049 and 150 subjects to treatment with GONAL-F) at 10-15 sites in China.

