This trial is designed to demonstrate non-inferiority of FE 999049 vs. GONAL-F with respect to the number of oocytes retrieved. The non-inferiority margin has been set to 3.00 oocytes, as this margin is regarded to be appropriate for demonstrating the efficacy of FE 999049 treatment in a conventional dosing regimen with a long GnRH agonist protocol. The margin of 3.00 oocytes is in line with the regulatory precedence in Europe for rFSH biosimilars,²¹ and is also a common clinical standard for clinical trials in China demonstrating equivalence between rFSH drug and comparator, e.g. GONAL-F to obtain regulatory approval from the National Medical Products Administration (NMPA).^{22,23,24} Furthermore, the mean number of oocytes retrieved with placebo (i.e. without stimulation) would be approximately 1, and the expected mean number of oocytes retrieved expected with GONAL-F (active control drug) will be approximately 10. Therefore, the efficacy difference between the active control and placebo would be approximately 9, implying that the M1 (defined in the regulatory guideline for clinical non-inferiority trials in China)²⁵ is considerably larger than 3.00. A successful non-inferiority result will therefore both ensure that the effect of FE 999049 is better than placebo and clinically equivalent to GONAL-F, according to regulatory precedence for rFSH biosimilars in Europe and China.^{22,23,24,26,27} Selection of endpoints is further discussed in Section 3.5.2.

Strict criteria have been incorporated in the design of this comparative trial to properly assess the effect of the interventions on treatment outcome. In general, standardisation of criteria, timing of assessments, procedures and interventions have to a great extent been incorporated in the design of this trial to minimise variation.^{28,29,30}

For safety reasons, only subjects with serum AMH concentrations of ≤ 35 pmol/L at screening are eligible for randomisation to treatment and treatment is limited by maximum doses of 20 μ g FE 999049 and 300 IU GONAL-F for a maximum of 20 days. Additional safety measures include cycle cancellation for subjects with ≥ 25 follicles with a diameter ≥ 12 mm or for safety concerns, as judged by the investigator, and transfer cancellation for subjects with retrieval of ≥ 20 oocytes.

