6.5 Stimulation

6.5.1 Stimulation Day 1

Stimulation day 1 visit takes place after downregulation is confirmed. The following must take place before randomisation to treatment:

- Ensure that the subject is still eligible for participation in the trial
- Check those inclusion and exclusion criteria that were not possible during screening
- Urine pregnancy test – must be negative
- Blood collection for central laboratory analysis of estradiol and progesterone
- Transvaginal ultrasound of uterus and ovaries (endometrial thickness, ovarian volume, number and size of follicles). If a cyst ≥ 10 mm is observed (functional or not), it should be punctured before treatment is initiated.^a If the cyst was present at the screening visit, it should have been recorded on the medical history form. If the cyst presented between screening and stimulation day 1, it should be recorded on the adverse event form.

^a Treatment can be initiated the same day. If puncture is not possible, the subject is not to be considered eligible for participation in the trial.

If the subject fulfils all inclusion and exclusion criteria, she will proceed to:

- Assessment of appropriate starting dose level (i.e. 10 µg FE 999049 / 150 IU GONAL-F or 15 µg FE 999049 / 225 IU GONAL-F) and allocation to the corresponding stratum.
- Randomisation to treatment (i.e. FE 999049 or GONAL-F) and assignment to the lowest available subject number within site and stratum.

Once the above has been completed, the following must be performed by the trial medication delegate. Care must be taken to ensure blinding of the investigator and other assessors.

- Dispense IMP according to randomisation and instruct the subject on how to administer the IMP
- Administer the 1st dose of IMP according to randomisation [administration of IMP takes place at the clinic and can be done by either the trial medication delegate or the subject under supervision by the trial medication delegate]:
 - If randomised to FE 999049; starting dose for the first 5 days is fixed at 10 µg or 15 µg according to investigator's assessment
 - If randomised to GONAL-F; starting dose for the first 5 days is fixed at 150 IU or 225 IU according to investigator's assessment
- Dispensing of GnRH agonist, as applicable

The IMP should preferably be administered at the same time each day during the stimulation period and the timing of the IMP administrations should be aligned with the GnRH agonist administrations.

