9.6.2 Primary Endpoint

The primary endpoint, number of oocytes retrieved, will be compared between FE 999049 and GONAL-F using a negative binomial model with treatment and dose level (10 µg/150 IU or 15 µg/225 IU) as factors. The absolute treatment difference in number of oocytes retrieved and the associated two-sided 95% confidence interval will be derived from the model estimates using the delta method. Non-inferiority will be considered confirmed if the lower limit of the 95% confidence interval for the difference between FE 999049 and GONAL-F is greater or equal than -3.00.

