9.6.3 Secondary Endpoints

Number of Follicles

Total number of follicles, and number of follicles ≥ 10 mm, ≥ 12 mm, ≥ 15 mm and ≥ 17 mm, on stimulation day 6 and at end-of-stimulation will (in separate analyses) be compared between FE 999049 and GONAL-F using the same negative binomial regression model as used for the primary endpoint.

Serum Concentrations of Estradiol and Progesterone

Serum concentrations of estradiol and progesterone on stimulation day 6 and at end-of-stimulation will (in separate analyses) be compared between FE 999049 and GONAL-F using analysis of covariance (ANCOVA) models with treatment and dose level as factors and with the serum concentration on stimulation day 1 as a covariate. Multiplicative models will be used, i.e. the serum concentrations will be log-transformed before analysis. The results of the analyses will be back-transformed and presented as estimated geometric means and mean treatment ratios. Values below the lower limit of quantification (LLOQ) will be estimated with LLOQ/2. Potential values above the upper limit of quantification (ULOQ) will be included as ULOQ.

Number of Fertilised Oocytes and Fertilisation Rate

Number of Fertilised oocytes will be compared between FE 999049 and GONAL-F using the same negative binomial regression model as used for the primary endpoint. The fertilisation rate (number of fertilised oocytes/number of oocytes) will be described for subjects with at least one oocyte retrieved.

Number of Embryos

Number of embryos and good-quality embryos will be compared between FE 999049 and GONAL-F using the same negative binomial regression model as used for the primary endpoint.

Total Gonadotropin Dose and Number of Stimulation Days

Total gonadotropin dose will be summarized by treatment and dose level. Number of stimulation days will be compared between FE 999049 and GONAL-F using an analysis of variance model with treatment and dose level as factors.

Pregnancy Endpoints (Positive β hCG rate, Clinical Pregnancy Rate, Vital Pregnancy Rate, and Ongoing Pregnancy Rate)

Pregnancy endpoints will be compared between FE 999049 and GONAL-F using a logistic regression model with treatment and dose level as factors. The results in terms of odds for pregnancy will be converted into proportions, difference in proportions, and a 95% confidence interval for difference in proportions using the delta method.

Implantation Rate and Ongoing Implantation Rate

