9.8 Pregnancy Follow-up

Live birth will be compared between FE 999049 and GONAL-F using the same method as for pregnancy endpoints. Follow-up data on neonatal health will be described. These data will be reported separately.

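### Randomisation is stratified by site, but the primary model leaves site out; if site carries clearly more than about 5% of the variance, the non-inferiority interval is slightly too wide

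*Combined protocol and SAP*

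**What the plan says.** Section 4.2.2 stratifies the randomisation by the investigator's choice of starting dose level and then adds: "Blocks will be maintained within trial sites, i.e. the randomisation will be stratified by trial site". Section 6.5.1 (Stimulation Day 1) describes the same allocation: "assignment to the lowest available subject number within site and stratum". The trial is planned "at 10-15 sites in China" (3.2).

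The primary comparison in 9.6.2, repeated in the synopsis, is made "using a negative binomial model with treatment and dose level" as its only factors. The absolute difference and its 95% interval come from the delta method, and the lower limit is compared with -3.00.

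The comparative secondary models also use dose level as their only stratification factor. The estradiol and progesterone ANCOVAs are fitted "with treatment and dose level as factors and with the serum concentration on stimulation day 1 as a covariate". The pregnancy endpoints are compared "using a logistic regression model with treatment and dose level as factors", and live birth "using the same method as for pregnancy endpoints" (9.8).

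Nothing in the text reviewed says how site enters the analysis or why it is left out. Section 9.6.1 defers detail to a separate SAP, which was not among the documents reviewed.

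**The concern.** Blocking within site balances the arms inside each site, so most between-site variation drops out of the treatment comparison. A model without site does not know this. It leaves that variation in the residual and reports a standard error larger than the real sampling variation of the estimate. In a non-inferiority trial the effect falls on the lower confidence limit, which sits further from the estimate than the design warrants. At stake is a small amount of power, and only if sites really differ in oocyte yield.

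**Working it through.** **Inputs from the protocol.** SD 7.5, margin 3.00, true difference 0, one-sided 2.5%, 133 per group for 90% power, 300 randomised (9.1); expected GONAL-F mean about 10 (3.5.1); 10-15 sites (3.2). No between-site variance is given, so the share of total variance due to site, ρ, is assumed at 0, 5, 10 and 15%. Site means then have an SD of 7.5·√ρ = 0, 1.7, 2.4 and 2.9 oocytes.

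**The plan's own figure.** n = 2·[7.5·(1.960 + 1.282)/3]² = 131.3, so 132 per group against the stated 133. Power is 90.4% at 133 and 93.4% at 150 per group. The figure reproduces. It uses the total SD, so leaving site out does not undermine it.

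**Idealised bound.** With exact balance within sites and no cost for fitting site terms, the residual SD is 7.5·√(1-ρ), and omitting site widens the interval by 1/√(1-ρ). At 150 per group the planned half-width is 1.960·7.5·√(2/150) = 1.697.

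| ρ | Half-width with site | Widening | Power, site omitted / included |
|---|---|---|---|
| 0% | 1.697 | 0% | 93.4 / 93.4% |
| 5% | 1.654 | 2.6% | 93.9 / 94.5% |
| 10% | 1.610 | 5.4% | 94.4 / 95.5% |
| 15% | 1.565 | 8.5% | 94.9 / 96.4% |

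**Simulation with realistic costs** (12,000 trials per scenario). Further assumptions:
- uneven enrolment: 10 sites of 70, 55, 45, 35, 28, 22, 17, 13, 9, 6, or 15 sites of 55, 43, 35, 29, 25, 21, 18, 16, 14, 12, 10, 8, 6, 5, 3;
- sites under 10 pooled;
- 40% of subjects at the higher dose level, with mean ratio 0.8;
- blocks of 4 within site and dose level, the last block incomplete;
- multiplicative site effects.

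The site model used predictions averaged over subjects and an HC3-type SE. The planned model used the maximum-likelihood SE.

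True difference 0:

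| ρ | Power, 10 sites: planned / site (change) | Power, 15 sites: planned / site (change) | Half-width change, 10 / 15 sites |
|---|---|---|---|
| 0% | 93.9 / 93.4 (-0.6) | 93.9 / 93.2 (-0.7) | +0.03 / +0.04 |
| 5% | 94.5 / 94.6 (+0.2) | 94.4 / 94.5 (+0.2) | -0.01 / 0.00 |
| 10% | 95.0 / 95.8 (+0.9) | 95.2 / 95.9 (+0.7) | -0.05 / -0.04 |
| 15% | 95.5 / 96.9 (+1.5) | 95.4 / 96.7 (+1.3) | -0.10 / -0.09 |

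Changes were taken before rounding; their Monte Carlo error is about 0.1 point. The planned half-width is 1.64-1.67.

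**Planned model against itself.** Reported SE over true SD of the estimate, 10 sites: 0.851/0.857 = 0.99 at 0%, 0.842/0.837 = 1.01 at 5%, 0.838/0.804 = 1.04 at 10%, 0.836/0.796 = 1.05 at 15%. With 15 sites: 0.850/0.853 = 1.00, 0.842/0.839 = 1.00, 0.837/0.811 = 1.03, 0.836/0.794 = 1.05.

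**False non-inferiority at a true difference of -3** (Monte Carlo error about 0.15 points):

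| Model and SE | 10 sites, ρ = 0/5/10/15% | 15 sites, ρ = 0/5/10/15% |
|---|---|---|
| Planned | 3.0/2.6/2.4/2.1% | 3.2/2.8/2.4/2.2% |
| Site, maximum-likelihood SE | 3.1/2.9/3.0/2.9% | 3.5/3.1/2.9/3.1% |
| Site, HC3-type SE | 2.8/2.6/2.6/2.5% | 3.0/2.6/2.5/2.6% |

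With fixed site terms the maximum-likelihood SE is 0.97-0.99 of the true SD, and the HC3-type SE is 1.00-1.02 of it.

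**The case against.** The strongest reply is that there is no defect. The protocol nowhere promises that every randomisation factor will enter the model. Where omitting site has an effect, it is conservative, which is the safe direction for a non-inferiority claim. That stands, and it is why this is a point to consider rather than an error.

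The gain rests on an assumed site share, and the protocol gives reasons to expect a small one. Standardised criteria, timing and procedures "have to a great extent been incorporated in the design of this trial to minimise variation" (3.5.1). Dose steps and limits are fixed, retrieval follows a follicle-size rule (6.6), and triggering and cancellation have stated criteria (Table 6-2). Against that, starting dose level and dose adjustment are left to the investigator (3.5.4, 3.5.3), as is some triggering and cancellation. Subjects without retrieval count as zero (9.6.1), so different cancellation habits would feed straight into the endpoint. The text settles neither view. If sites differ partly in dose mix, the dose-level term already absorbs some of the difference.

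The power comparison also changes two things at once, the site terms and the type of SE. That is fair, but comparing the planned model with its own sampling SD does not have this problem, and it shows an SE 3-5% too large at a 10-15% share.

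A site-adjusted sensitivity analysis alone would be simpler. It would leave the decision interval unchanged, so it would recover none of the lost precision. Lastly, the separate SAP may already handle site. That cannot be checked here, and it would not change what 9.6.2 now says.

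**Conclusion.** The mismatch between 4.2.2 and 9.6.2 is real and its consequence is small. If site explains clearly more than about 5% of the variance, the interval is slightly conservative: about 0.04-0.10 oocytes of half-width and 0.7-1.5 points of power at a 10-15% share. At 5% there is essentially nothing to gain, and at 0% adding site costs 0.6-0.7 points. Power stays above 93% in every scenario examined. The size depends on the assumed site shares, enrolment pattern, dose mix and block size.

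A reader might infer more than this, and the documents do not support it:
- **The primary analysis is invalid or too lenient because of the omission.** Leaving site out does not bias the difference under within-site allocation, and false non-inferiority falls as site differences grow.
- **The trial is underpowered or mis-sized.** The 133 per group reproduces, and it already uses the total SD.
- **Any site difference widens the interval appreciably.** The simulated change at a 5% share is 0.00 to 0.01 oocytes.
- **The secondary models suffer a loss of the same size.** They omit site too, but no size has been worked out for them.

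**What to change.** In 9.6.2 and the synopsis, before unblinding:
- Add site as a main effect beside treatment and dose level in the primary negative binomial model. Main effects are more practical than site-by-dose cells: 10-15 sites by two dose levels gives 20-30 cells, or only 10-15 subjects per cell on average.
- Pool small sites by a fixed rule, for example those with fewer than 10 randomised.
- Obtain the absolute difference by averaging predicted counts over subjects.
- Use a small-sample-corrected or HC3-type variance, because the plain maximum-likelihood SE with fixed site terms is about 1-3% too small and gave 2.9-3.5% false non-inferiority.
- Keep the dose-level-only model as a sensitivity analysis.

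The cost is a few lines of text, a pooling rule, a non-default variance and about 0.6-0.7 points of power if sites do not differ. A random site effect and extension to the secondary endpoints were not tested and are not part of this proposal. If the separate SAP already includes site, the only action is to align 9.6.2 with it.
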